4.4 C - Reactive Protein (CRP)

CRP will be summarized for measurements made at Screening, Day 14, and for changes from Screening to Day 14. CRP is not considered a safety endpoint. Therefore, CRP will be summarized in the mITT Analysis Set .

4.5 Exploratory Endpoints

The following will be assessed as exploratory endpoint.

• Distribution of observed mSOFA at Days 21 and 28.

4.6 Exploratory Subgroup Analysis

Exploratory subgroup analysis will be performed. For these exploratory analyses, primary efficacy, selected secondary efficacy, selected safety tables will be repeated stratified according to the following classifications:

- 1. Age \geq 65 years vs. \leq 65 years
- 2. Gender
- 3. BMI (<30 versus 30-<40 vs. ≥ 40 kg/m²),
- 4. White vs. non-white
- 5. AKI Status (Any AKI, Stage 2/3 AKI, non-AKI).
- 6. Patients Achieving Freedom from Durable Loss of Renal Function vs. not (among patients presenting with Stage 2 or Stage 3 AKI)
- 7. Presence of cardiovascular organ failure (SOFA component >=3 at baseline) vs. those without CV organ failure (except SOFA related tables)
- 8. Presence of respiratory organ failure (SOFA component >=3) at baseline vs. those without (except SOFA related tables)
- 9. LRINEC ≥ median vs. LRINEC < median
- 10. ANAYA ≥ median vs. ANAYA < median
- 11. APACHE II ≥ 10 vs. APACHE < 10
- 12. Type of bacteria (Gram-positive vs. Gram-negative and possibly a 'mixed' type if needed), list to be provided by Sponsor and other prevalent pathogens.
- 13. Prevalent sub types and classes of identified pathogens
- 14. Bacteremic vs. non-bacteremic (blood culture)

The results for any subgroup analysis will not be interpreted if there are fewer than five patients in either treatment group within that subgroup analysis.

The following tables will be provided for stratifications 1 through 11 listed above. These tables are described in more detail below. Only the primary endpoint table (Table 14.2.1.1) will be stratified for the subgroups 12, 13, and 14.

14.2.1.1	Comparisons of the Percentages of Patients Achieving Primary Composite Clinical Success Endpoint (NICCE) and its Components mITT Analysis Set†
14.2.1.2	Comparisons of the Percentages of Patients Achieving Conditional Co-Primary Endpoint (CCPE) and its Components mITT Analysis Set†
14.2.2.2	Modified SOFA Total Score and Organ Specific Scores Over Time to Day 14 Last Observation Carried Forward (LOCF) mITT Analysis Set†
14.2.2.4	Modified SOFA Total Score and Organ Specific Scores Over Time to Day 14 Change from Day 0 (Screening) - Last Observation Carried Forward (LOCF) mITT Analysis Set†
14.2.2.6	Modified SOFA Total Score and Organ Specific Scores Over Time to Day 14 Change from Day 1 - Last Observation Carried Forward (LOCF) mITT Analysis Set†
14.2.4.1	Critical Care and Hospital Stay Parameters Over Days 1 to 28 By Treatment Group mITT Analysis Set†
14.2.5.1	Cumulative Number of Debridements to Days 7, 10, and 14 By Treatment Group mITT Analysis Set†
14.2.5.2	Percentage of Patients Requiring 1, 2, 3, >=3, and >3 Debridements Through Day 14 By Treatment Group mITT Analysis Set†
14.2.6.2.1	Numbers and Percentages of Subjects Achieving Freedom from Durable Loss of Renal Function and Improvement in Durable Loss of Renal Function at Day 28 Algorithmic Determination of Reference Creatinine Algorithmic Determination of AKI at Screening Algorithmic Determination of Day 28 Status Using LOCF& Among mITT Subjects with Stage 2 or Stage 3 Screening AKI Using Algorithmic Reference
14.3.1.1	Summary of Treatment-Emergent Adverse Events (TEAEs) Overall and by Treatment Group As Treated (Safety) Analysis Set†

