1.1 Revisions to SAP in Version 4.0

The prior version of this SAP was Version 3.0, September 14, 2015. The final updates included in this Version 4.0 of the SAP were made while treatment allocation remained blinded.

There are two primary types of updates. The first type of update relates to the secondary efficacy endpoints concerning AKI. The AKI endpoints are now harmonized with the AKI endpoints to be used in the currently enrolling AKI pivotal trial. The primary efficacy endpoint from the ongoing AKI trial (ATB-203) has now been specified formally as the **key secondary efficacy endpoint** for this trial to allow the results from this trial (ATB-202) to support those from the AKI trial.

This endpoint is freedom from durable loss of renal function defined as alive, free of dialysis, and less than a 37% loss of estimated Glomerular Filtration Rate (eGFR; measured with the Modification of Diet in Renal Disease (MDRD) formula from the patient's reference eGFR)) at Day 28.

The second type of update generally relates to changes made to accommodate the needs of the NDA and future integrated summaries of safety and effectiveness in light of the observation that ATB-202 will form the bulk of the safety population for the NDA.

¹ ICH E9 Expert Working Group. Statistical Principles for Clinical Trials: ICH Harmonized Tripartite Guideline. Statistics in Medicine 1999; 18:1905–1942.

2 Key Elements of the Analysis Plan

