2.3 Key Secondary AKI Endpoint

The same endpoint that is being currently employed in the ongoing ATB-203 study of AKI in sepsis will be evaluated as the key secondary endpoint in this study. The key secondary endpoint is *freedom from durable loss of renal function at Day 28*. Only subjects with AKI Stage 2 or Stage 3 prior to initial drug dosing will be included in this comparison. The key secondary endpoint requires:

- (i) Alive at Day 28,
- (ii) Free of dialysis at Day 28, and
- (iii) Less than a 37% loss of estimated Glomerular Filtration Rate (eGFR; measured with the Modification of Diet in Renal Disease (MDRD) formula from the patient's reference eGFR)) at Day 28.

Reference creatinine values, baseline AKI stage and percentage loss of eGFR at Day 14 and 28 will be determined through algorithmic determination (see details below). Percentage loss of eGFR determined algorithmically will be based on a comparison of eGFR at screening compared to an algorithmically determined reference creatinine value. A sensitivity analysis will utilize an independently adjudicated reference value to determine baseline eGFR.

To control type 1 error for the key secondary efficacy endpoint, superiority of Reltecimod relative to placebo in terms of freedom from durable loss of renal function at Day 28 among those presenting with Stage 2 or Stage 3 AKI will only be interpreted as a confirmatory hypothesis test if $p \le 0.01$ for the primary endpoint (NICCE) and $p \le 0.05$ for the co-primary endpoint (CCPE).

Otherwise, treatment group comparisons in terms of the key secondary efficacy (AKI) endpoint will be interpreted as a descriptive endpoint. An unadjusted chi-square test using a two-sided type 1 error of α =0.05 will be used to test superiority of Reltecimod relative to placebo for the key secondary AKI endpoint.

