4.1 AKI Related Endpoints

4.1.1 Freedom from Durable Loss of Renal Function at Day 28

The same endpoint that is being currently employed in the ongoing ATB-203 study of AKI in sepsis will be the key secondary endpoint in this study. Only subjects with AKI Stage 2 or Stage 3 prior to drug dosing will be included in this comparison.

The key secondary AKI endpoint is *freedom from durable loss of renal function at Day 28* defined as alive, free of dialysis, and less than a 37% loss of estimated Glomerular Filtration Rate (eGFR; measured with the Modification of Diet in Renal Disease (MDRD) formula from the patient's reference eGFR)) at Day 28.

Reference creatinine values, baseline AKI stage and percentage loss of eGFR at Day 14 and 28 will be determined through algorithmic determination (see details below). Percentage loss of eGFR determined algorithmically will be based on a comparison of eGFR at screening compared to an algorithmically determined reference creatinine value. A sensitivity analysis will utilize an independently adjudicated reference value to determine baseline eGFR.

To control type 1 error for the key secondary efficacy endpoint, superiority of Reltecimod relative to placebo in terms of freedom from durable loss of renal function among those with Stage 2 or Stage 3 AKI prior to dosing, will only be interpreted as a confirmatory hypothesis test if p \leq 0.01 for the primary endpoint (NICCE) and p \leq 0.05 for the co-primary endpoint (CPEP). Otherwise, treatment group comparisons in terms of the key secondary efficacy (AKI) endpoint will be interpreted as a descriptive endpoint. An unadjusted chi-square test using a two-sided type 1 error of α =0.05 will be used to test superiority of Reltecimod relative to placebo for the key secondary AKI endpoint.

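### SAP 4.6 item 6 compares the arms within strata of the Day 28 renal endpoint, a post-dose outcome that includes survival

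*SAP*

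**What the plan says.** SAP 4.6 lists 14 classifications for exploratory subgroups and says that "primary efficacy, selected secondary efficacy, selected safety tables will be repeated stratified according to the following classifications". Item 6 is "Patients Achieving Freedom from Durable Loss of Renal Function vs. not (among patients presenting with Stage 2 or Stage 3 AKI".

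The section continues: "The following tables will be provided for stratifications 1 through 11 listed above". Item 6 therefore receives the whole set:

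- NICCE (14.2.1.1) and CCPE (14.2.1.2)
- three mSOFA tables (14.2.2.2, 14.2.2.4, 14.2.2.6)
- critical care (14.2.4.1) and debridements (14.2.5.1, 14.2.5.2)
- the AKI endpoint itself (14.2.6.2.1)
- one safety table, the TEAE summary (14.3.1.1)

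SAP 10 repeats the table list for the subgroups already named and adds forest plots of NICCE, CCPE and the AKI endpoint (Figures 47 to 49 in Appendix 4).

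SAP 4.1.1 gives the renal endpoint as "defined as alive, free of dialysis, and less than a 37% loss of estimated Glomerular Filtration Rate", assessed at Day 28. SAP 2.3 makes it the key secondary endpoint, lists "Alive at Day 28" as its first requirement, and says a chi-square test "will be used to test superiority of Reltecimod relative to placebo for the key secondary AKI endpoint". The only pre-dose part of item 6 is the restriction to Stage 2/3 AKI; SAP 4.1.1 says of the key secondary comparison, "Only subjects with AKI Stage 2 or Stage 3 prior to drug dosing will be included in this comparison".

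**The concern.** A treatment comparison within a subgroup is protected by randomisation only if the subgroup is fixed before treatment. Item 6 is fixed up to 28 days after dosing, by an outcome that the trial itself tests for a treatment effect. If the drug moves patients from failing to achieving the renal endpoint, achievers on active are a different mix from achievers on placebo, and so are non-achievers. The difference between arms then mixes any drug effect with that change in case mix.

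The classifier also shares a component, survival to Day 28, with both NICCE and CCPE, so part of what is tabulated is already settled by the split.

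What is at stake is interpretation. These outputs would appear in the same tables and forest plots as valid baseline subgroups, and a renal benefit could show up as an apparent disadvantage on NICCE in both strata.

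**Working it through.** The SAP gives no figure for this analysis, so there is none to reproduce. The structural part needs no assumptions. The numerical part is illustration only.

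**1. Cells fixed by definition (patients presenting with Stage 2/3 AKI).**

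| Quantity | Achievers | Non-achievers |
|---|---|---|
| Alive-at-Day-28 component of NICCE and CCPE | 100% in both arms | not fixed |
| Deaths by Day 28 | none | all of them |
| Freedom-from-loss row of Table 14.2.6.2.1 | 100% vs 100% | 0% vs 0% |
| Improvement row of the same table (SAP 4.1.3) | – | not fixed |

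Items 7 and 8 are defined by SOFA components and carry an exception for SOFA-related tables. Item 6 carries no exception, even for its own endpoint table.

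**2. Mechanism, checkable by hand (all rates assumed).** Suppose 60% achieve the renal endpoint on either arm, 10% only on active and 30% on neither. Let their NICCE rates be 0.6, 0.3 and 0.1, the same in both arms. The overall NICCE rate is 0.36 + 0.03 + 0.03 = 0.42 in each arm, so the true effect is zero.

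- Achievers: active (0.36 + 0.03)/0.70 = 0.557; placebo 0.600; difference −0.043.
- Non-achievers: active 0.100; placebo (0.03 + 0.03)/0.40 = 0.150; difference −0.050.

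Varying the active-only group from 5% to 20%, at the expense of those who achieve on neither arm, gives −0.023 to −0.075 among achievers and −0.025 to −0.100 among non-achievers.

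**3. A smoother model (all inputs assumed).** Severity S is standard normal. Renal success has logit 0.6 + b·(active) − 1.0·S. The NICCE-like outcome has logit −0.2 − 1.2·S in both arms, which is 46.1% overall in each arm. Integrating over S gives:

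| b | Renal success, placebo / active | Achievers, active vs placebo | Non-achievers, active vs placebo |
|---|---|---|---|
| 0.2 | 62.2% / 66.0% | 52.8% vs 53.5% (−0.7) | 33.2% vs 34.0% (−0.8) |
| 0.4 | 62.2% / 69.7% | 52.1% vs 53.5% (−1.4) | 32.5% vs 34.0% (−1.5) |
| 0.8 | 62.2% / 76.3% | 50.8% vs 53.5% (−2.7) | 31.1% vs 34.0% (−2.9) |

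Check at b = 0.8: active 0.763 × 0.508 + 0.237 × 0.311 = 0.461; placebo 0.622 × 0.535 + 0.378 × 0.340 = 0.461. Simulating the same model gives about −0.6 to −3 points, the gap being simulation error.

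**4. Could the trial see it?** Take the extreme case in which all 290 patients (145 per arm) had Stage 2/3 AKI. The 95% half-width is 1.96·√(p₁q₁/n₁ + p₀q₀/n₀).

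- Achievers at b = 0.8, n = 110.7 and 90.2: 1.96·√(0.508·0.492/110.7 + 0.535·0.465/90.2) = 13.9 points.
- Non-achievers at b = 0.8, n = 34.3 and 54.8: 1.96·√(0.311·0.689/34.3 + 0.340·0.660/54.8) = 19.9 points.
- With an assumed 50 such patients per arm, the half-widths are about 24 and 34 points.
- The largest figure in step 2, −10 points among non-achievers, has a half-width of 1.96·√(0.10·0.90/29 + 0.20·0.80/58) = 15 points.

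None of these shifts would stand out from chance at this trial's size.

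**The case against.** The strongest reply is that nothing depends on item 6. SAP 4.6 is headed as exploratory, and SAP 5.5 treats all subgroup results as supportive or hypothesis-generating. SAP 5.6 controls type 1 error only for NICCE, CCPE and the key secondary endpoint. No item 6 table enters the success criterion (SAP 2.2) or the futility rule (SAP 2.7). The illustrated bias is also small beside its interval. All of this stands, and it limits the seriousness of the point. It does not rescue the analysis: an exploratory label warns about chance and multiplicity, not systematic bias, and the SAP 4.6 rule against interpreting subgroups with fewer than five patients per arm does not touch it either.

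A reader might infer more than the documents support:

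- *That the confirmatory results are compromised.* They are not; item 6 feeds none of them.
- *That any drug effect causes the bias.* In these models it arises only if the drug changes the renal outcome.
- *That every death in the trial falls in one stratum.* This holds only for deaths by Day 28 among patients presenting with Stage 2/3 AKI; other patients are outside item 6.
- *That Table 14.2.6.2.1 becomes empty, or reads 100% against 0% between arms.* The freedom-from-loss row is identical in both arms within each stratum, and the improvement row is not fixed among non-achievers.
- *That item 6 is the only classification in doubt.* Item 5 does not say when AKI status is taken. The SAP has both a pre-dose screening stage (4.1.4.2) and an adjudicated maximal stage over the first 7 days (4.1.2).
- *That the trial would report a visible false harm signal.* Steps 2 to 4 do not show that.

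Item 6 also does not print Day 28; that reading comes from the endpoint's definition. The Day 14 version in SAP 4.1.3 would be post-dose too.

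**Conclusion.** The point holds as a defect in an exploratory analysis. Item 6 uses a post-dose efficacy endpoint that includes survival as a subgroup factor for treatment comparisons. That rests on the SAP's own definitions alone, as do the fixed cells in step 1. Bias follows if the drug changes the renal outcome and patients moved by it differ in prognosis from the others in their stratum.

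Its size cannot be derived from the documents. With no true effect on a NICCE-like outcome, the log-odds model gives about 0.7 to 3 points against active in both strata, and the coarser three-class example gives 2.3 to 10. A renal harm instead of a benefit would reverse the sign. The confirmatory conclusions stand either way. The change is worth making because the tables cannot answer a treatment question and would sit beside subgroups that can.

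**What to change.** Delete item 6 from the classification list in SAP 4.6. SAP 10 has no subgroup list of its own; its tables and Figures 47 to 49 refer back to 4.6 and follow from the deletion.

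Keep Table 14.2.4.5 (critical care and hospital stay by renal outcome, SAP 8.9) and label it descriptive. It relates one outcome to another without comparing arms.

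Add to item 5 that AKI status means screening, pre-dose AKI as determined in SAP 4.1.4.2, not maximal AKI over the first 7 days. That leaves a valid renal subgroup.

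The cost is a few words of SAP text and fewer tables. The subgroups named in protocol 9.2.5 do not include item 6, so no protocol commitment is lost.

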4.7 Microbiology

By-Pathogen and By-Patient bacteriological responses will be summarized as follows:

- o *By-Pathogen Bacteriological Response:* The by-pathogen bacteriological response for each causative organism identified at baseline (BL) will be defined as follows:
 - Eradication: BL causative organism cannot be isolated from any culture(s) obtained from a debridement performed on or after study Day 3.
 - Persistence: The BL causative pathogen is isolated from a debridement performed on or after study Day 3.
- o *By-Patient Bacteriological Response:* The by-patient bacteriological response will be determined according to the following definitions:
 - Eradication: All BL causative organism(s) have a response of Eradication.
 - Persistence: All or some BL causative organism(s) have a response of Persistence.

Presence of pathogens will be determined using blood and tissue cultures. Treatment group comparisons of response rates will only be performed if there at least 5 instances of a unique pathogen in both groups and are limited to patients with microbiological samples at screening and at follow-up (i.e., day 3). By-patient microbial responses will be based on worst response.

Pathogens will also be categorized into Gram-positive / Gram-negative and into aerobic and anaerobic sub types.

Prevalent sub types and classes of identified pathogens will be used in sub group analyses of clinical response as described above.

5 Analysis Approaches

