6.2.15 Microbiology

Microbiological testing will follow the SoC of treatment of NSTI patients. At the time of initial surgical exploration, and if surgical debridement is performed on study Day 3, a tissue sample will be cultured by the local microbiology laboratory.

The deep tissue specimens will be obtained at the time of the first debridement at the operating room at the study site medical center. Antibiotics received prior to the primary surgical debridement will be identified as well as antibiotics received during the study evaluation window of Days 1-28.

A specimen of infected tissue will be taken from the infected area, will be placed in a sterile container and transported by hand to the local designated clinical microbiology laboratory at the institution and according to the approved methods of each medical center. The specimens will then be processed as soon as possible by homogenization, the homogenate will be Gram stained, and cultured under 2 different conditions for testing of aerobic and anaerobic pathogens

Cultures of the NSTI wound will be obtained according to the schedule of events on Section 15.1. Bacterial isolates obtained from the patients in the study, and considered to be pathogens will be identified by genus and species using the methods established in the *Manual of Clinical Microbiology*⁴⁰. Results will be used to categorize patients according to microbiology organism group (Gram-positive, Gram-negative, anaerobic, mixed infection).

Susceptibility testing will be performed on all aerobic pathogens according to clinical laboratory standards institute (CLSI) criteria.

Blood culture for both aerobic and anaerobic bacteria will be taken during screening process. Repeat blood cultures for microbiology will also be obtained according to physician discretion, if the patient is suspected to have a new or progressive infection (if deterioration in the hospitalized patient's condition is observed (e.g. spiking a fever).

Bacterial isolates identified as *Streptococcus pyogenes* or *Staphylococcus aureus* will be stored frozen at the site and shipped to the Central Microbiology Laboratory (IHMA, Schaumburg, IL) for future testing. Instructions for freezing, storage and shipping of the bacterial isolates can be found in a separate Laboratory Manual for the study.

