7.2 Secondary Measures

- 5 component clinical composite endpoint but with mSOFA ≤ 1 at Days 21 and 28
- Distribution of mSOFA scores at Days 14 and 21
- Kaplan-Meier analysis of the time to resolution of mSOFA score to ≤1 with censoring at Day 14
- Single components of the composite end point
 - Alive at Day 28
 - Number of patients with debridements by Day $14 \le 3$
 - Number of amputations (excision to a joint space) (done after first debridement)
 - mSOFA score on Day $14 \le 1$
 - Reduction of \geq 3 score points between Baseline and Day 14 mSOFA score.
 - Critical care and hospital stay parameters, to be measured until Day 28
 - o ICU-free days
 - Days in ICU
 - Days on ventilator
 - Ventilator free days
 - Vasopressors days/ Vasopressors free days
 - Hospital length of stay (days)
- Clinical local parameters:
 - Number of debridement to days 7, 10, 14 and 28
 - Proportion of patients needing (up to Day 14):
 - 1. only one debridement to control the infection
 - 2. \geq 2 debridements to control the infection
 - 3. \geq 3 debridements to control the infection

- Clinical systemic parameters:
 - Evaluation of organ function over time, using mSOFA score
 - Recovery from AKI

7.3 Exploratory Measures:

- Evaluation of blood leukocyte transcriptome (RNA expression) profiling in patients with NSTI and compare genomic profile in patients treated with AB103 versus placebo
- Evaluation of the clinical response by baseline pathogen
- Evaluation of the microbiological outcome in the microbiological evaluable population
 - *By-Pathogen Bacteriological Response:* The by-pathogen bacteriological response for each causative organism identified at baseline (BL) will be defined as follows:
 - Eradication: BL causative organism cannot be isolated from any culture(s) obtained from a debridement performed on or after study Day 3.
 - Persistence: The BL causative pathogen is isolated from a debridement performed on or after study Day 3.
 - *By-Patient Bacteriological Response:* The by-patient bacteriological response will be determined according to the following definitions:
 - Eradication: All BL causative organism(s) have a response of Eradication.
 - Persistence: All or some BL causative organism(s) have a response of Persistence.
- Evaluation of plasma and urinary biomarkers in patients with AKI
- Data (including financially related data) will be gathered to evaluate possible health economic outcomes from the study, including but not limited to:

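### Bacteriological response is scored on debridement cultures alone, although the SAP determines pathogens from blood and tissue, so an organism still growing in blood can be scored as eradicated

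*SAP*

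**What the plan says.** SAP 4.7 assigns a response to each causative organism identified at baseline. Success is "Eradication: BL causative organism cannot be isolated from any culture(s) obtained from a debridement performed on or after study Day 3". Protocol 7.3 gives the same eradication rule, and its failure rule, which SAP 4.7 shares, is "Persistence: The BL causative pathogen is isolated from a debridement performed on or after study Day 3". Neither definition mentions blood.

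After the definitions, SAP 4.7 adds: "Presence of pathogens will be determined using blood and tissue cultures". The sentence does not say whether it applies to baseline, to follow-up, or to both. Two other parts of the SAP use both sources: the baseline microbiology table (14.1.3.5) and the pathogen assignment listing (16.2.8.12.2).

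At patient level the SAP states: "By-patient microbial responses will be based on worst response". Treatment comparisons need at least 5 instances of a pathogen in both groups, and samples at screening and at follow-up, which the SAP glosses as Day 3. The specimen type of the follow-up sample is not stated.

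On sampling, Protocol 6.2.15 provides a baseline blood culture: "Blood culture for both aerobic and anaerobic bacteria will be taken during screening process". Later ones are not scheduled: "Repeat blood cultures for microbiology will also be obtained according to physician discretion, if the patient is suspected to have a new or progressive infection". Tissue is cultured at the first debridement and again if a debridement takes place on Day 3. A schedule footnote adds repeat tissue culture at later debridements when the Day 3 culture is positive.

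**The concern.** The specimens that can identify a pathogen are wider than the specimens that can show it has persisted. A bloodstream organism can therefore enter the denominator at baseline, but only a tissue culture can score it as a failure afterwards. No rule says how a positive blood culture on or after Day 3 is scored.

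What is at stake is the meaning of the eradication rate. A measure in which a positive follow-up blood culture never counts as persistence cannot support a statement about bacterial clearance in general. It describes clearance from debrided tissue. The SAP itself treats bacteraemia as worth separating, since SAP 4.6 lists bacteraemic versus non-bacteraemic as a NICCE subgroup. The error would lie in classifying the outcome, which is a different matter from who gets sampled at follow-up.

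**Working it through.** The plan gives no figure to reproduce here, so the check applies the definitions of SAP 4.7 and Protocol 7.3, as written, to each combination of baseline source and follow-up result.

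| Case | Baseline source | Debridement culture on or after Day 3 | Blood on or after Day 3 | Score as written |
|---|---|---|---|---|
| 1 | Any | Grows the organism | Any result | Persistence |
| 2 | Any | Taken, does not grow it | Grows it | Eradication |
| 3 | Blood only | Taken, does not grow it | Negative or not taken | Eradication |
| 4 | Any | None taken | Positive, negative or not taken | Eradication wording met vacuously |

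Case 2 follows because Persistence requires isolation from a debridement, so a positive blood culture does not meet it. Case 3 follows because the organism is judged at a site where it was not found at baseline, while the site where it was found need not be re-cultured. The by-patient rule takes the worst by-pathogen response. When the only evidence of persistence is in blood, no by-pathogen response is Persistence, and the patient is also scored as eradicated.

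Next, does anything else in the documents repair cases 2 and 3?

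- The follow-up-sample restriction removes unsampled patients from comparisons. It does not require the follow-up specimen to match the baseline source, so cases 2 and 3 remain.
- The Protocol refers to a microbiological evaluable population (2.3 and 7.3), but neither list of analysis sets (Protocol 9.2.2, SAP 2.6) defines one.
- The SAP table list contains no eradication or persistence table. The wording of SAP 4.7 is all a programmer would have.
- Suppose the sentence on blood and tissue is read as covering follow-up. A blood isolate on or after Day 3 then shows the pathogen to be present, while the definition beside it returns Eradication. The text conflicts with itself on that reading.

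On size, one step of arithmetic is available. At the minimum count of 5 instances in a group, one reclassified organism changes that group's rate by 1/5 = 20 percentage points. This shows how coarse the comparison is at its threshold. It does not estimate bias, because the documents give no rate of baseline bacteraemia, of blood-only organisms, or of repeat cultures.

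**The case against.** Several points on the other side carry weight.

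**Blood-only organisms.** It is tempting to say these are eradicated automatically. That assumes a blood-only isolate is assigned as a causative organism. The schedule footnote on tissue says first-debridement tissue is used for pathogen identification, and the assignment rules behind the listing are not in the documents. Within a comparison, a sampled debridement must also fail to grow the organism. The point stands only with both conditions.

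**No debridement on or after Day 3.** A reader might infer that such patients are counted as eradicated. The only scheduled Day 3 specimen is debridement tissue, so the Day 3 sample restriction probably removes them from comparisons. Case 4 matters only if a discretionary blood culture is accepted as the follow-up sample, which the text neither says nor rules out.

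**Persistent bacteraemia lost altogether.** This goes too far. Infection events have their own table (SAP 9.1.6), and blood cultures are listed by patient. The adverse event route is incomplete, because Protocol 8.5 and 8.5.1 name bacteraemia among disease-related events that need not be reported as adverse events. The gap nevertheless belongs to this measure, not to the whole trial.

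**A number for the effect.** One could assume that 20–30% are bacteraemic at baseline and that 5–15% of those regrow the organism, giving 0.20 × 0.05 = 1% to 0.30 × 0.15 = 4.5% of compared patients. Both rates are assumed. The product also requires that a discretionary culture was drawn and the debridement culture was negative, so it is an upper bound under those assumptions and says nothing about this trial.

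None of this removes case 2, or the conflict between the sentence on specimens and the definitions.

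**Conclusion.** The point holds as a defect of definition. As written, a baseline organism growing in blood on or after Day 3 is scored as eradicated when the debridement culture is negative. A blood-only baseline organism that is assigned as causative is scored as eradicated unless a later debridement grows it. The alternative reading of the specimen sentence contradicts the definitions, so the text needs reconciling either way.

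The consequence is small. The measure is exploratory, and no alpha or primary, co-primary or key secondary result depends on it. Repeat blood cultures are discretionary, so few patients may be affected. A reader might infer that the analysis would favour an arm with more persistent bloodstream infection. The documents do not support that: they contain nothing to suggest different rates between arms, and blinding gives no obvious reason for different culturing. This is a worthwhile clarification, not a threat to the trial's conclusions.

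**What to change.** In SAP 4.7, with matching wording in Protocol 7.3:

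1. Define Persistence as isolation of the baseline organism from any debridement or blood culture on or after Day 3.
2. State that the follow-up sample required for treatment comparisons is a debridement culture on or after Day 3, except that a positive blood culture alone counts as Persistence.
3. Report organisms found only in blood at baseline separately.
4. Show by arm the number of patients bacteraemic at baseline, the number with a repeat blood culture, and the number positive.

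Do not require a follow-up blood culture for Eradication of an organism found in blood. Repeat cultures are triggered by suspected new or progressive infection, so such a rule would keep mainly deteriorating patients in the rate.

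The cost is wording and some re-coding, best settled before unblinding. There are three downsides. Blood-based persistence will be incompletely ascertained. The exception in item 2 lets patients without a debridement culture enter only as failures, so their number should be shown by arm. The sponsor must also confirm that repeat blood culture results are entered in the database: the SAP has a blood culture listing, but the Protocol's post-screening visit lists do not mention collecting these results.
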